7.1.1 Clinical Events Committee

In order to apply some level of consistency and standardization, all potential primary safety endpoints will be adjudicated by a CEC. The CEC can combine AEs reported separately into a

single AE, can change the event description (i.e., the term used to report the AE) and can change the status of the reported event to a non-AE.

Any adjudicated event, including changed event descriptions, will be MedDRA-coded.

7.2 Partner Reported Pregnancy

Data from the Pregnancy Report Form will be listed, if applicable.

7.3 Laboratory Tests (Hematology, Serum Chemistry, and Urinalysis)

Hematological testing will include complete blood count (CBC), white blood cells (WBC) differential (absolute and percentage), hemoglobin, hematocrit, and platelet count.

Serum chemistry testing will include basic metabolic panel (Glucose, Sodium, Potassium, Chloride, Bicarbonate, Blood Urea Nitrogen (BUN), Creatinine, Calcium), comprehensive hepatic panel (Albumin, Alkaline Phosphatase, Total Protein, Alanine Aminotransferase (ALT), Aspartate Aminotransferase (AST), Gamma-Glutamyl Transferase (GGT), Direct Bilirubin, Total Bilirubin), and Creatine Kinase. Creatine Kinase isoenzymes (CK – Total, CK – BB, CK – MB, and CK – MM) will be included in displays as serum chemistry parameters.

Urinalysis analytes that will be tested include appearance, bilirubin, color, nitrite, occult blood, pH, protein, specific gravity, glucose, ketones, red blood cells (RBC) and WBC. If required, microscopic analysis of sediment will be performed and reported per occurrence.

For hematology, serum chemistry, and urinalysis quantitative tests, summary statistics will be presented for the observed values at each visit. Summary statistics will also be presented for the change from baseline values to each post-baseline visit. Scheduled assessments will be summarized, and unscheduled events will only be listed.

For all tests, results will be displayed in subject listings, with those values falling outside the laboratory reference range flagged. Laboratory reference ranges will be provided by the laboratory site(s) and will be included in an appendix of the clinical study report.

7.4 Vital Signs, Height, Weight and BMI

Vital signs will include systolic and diastolic blood pressure, heart rate, respiratory rate, body temperature and pulse oximetry (SpO₂). Pre-infusion observed values and changes from baseline will be summarized at each post-baseline visit. Scheduled assessments will be summarized, and unscheduled events will only be listed.

Listings of vital signs, ulna length, height, weight, and BMI will be provided. Height will either be measured (i.e., standing height) or calculated from the subject's ulna length.

7.5 12-Lead Electrocardiograms

All 12-lead electrocardiogram (ECG) results will be displayed in subject listings.

8 DEVIATIONS FROM STATISTICAL METHODS IN THE PROTOCOL

This final version 3.0 of the statistical analysis plan (SAP) supersedes all previous versions.

There were no changes to the conduct of the study since the last protocol amendment. Analyses planned but not performed and the rationales for the changes are as follows.

The following exploratory efficacy endpoints will not be analyzed:

- High-level (shoulder) dimension of the PUL 1.2;
- Distal-level (wrist and hand) dimension of the PUL 1.2;
- High-level (shoulder) dimension of the PUL 2.0;
- Distal-level (wrist and hand) dimension of the PUL 2.0;
- Grip strength, percent predicted, at Months 3, 6, 9, and 12;
- Tip-to-tip pinch strength, percent predicted, at Months 3, 6, 9, and 12;
- Key pinch strength, percent predicted, at Months 3, 6, 9, and 12;
- Elbow flexion strength, percent predicted, at Months 3, 6, 9, and 12;
- PODCI scales (subject and parent) at Months 3, 6, 9, and 12;
- Parent/caretaker-reported DMD-LMS at Months 3, 6, 9, and 12;
- NSAA at Months 3, 6, 9, and 12;
- 10MWRT at Months 3, 6, 9, and 12;
- Incidence of loss of ambulation (10MWRT > 30 seconds) at Months 3, 6, 9, and 12;
- Biomarkers at Months 3, 6, 9, and 12;
- Resource utilization, including hospitalizations for orthopedic injury or surgery and for pulmonary infections, over the course of the trial.

Originally, it was planned to perform a supportive analysis of the primary efficacy endpoint on the mITT Population. However, it was discovered that the mITT Population is equivalent to the ITT Population, so analyses of efficacy will only be performed on the ITT and PP populations.

Also, originally, it was planned to perform the secondary and exploratory efficacy endpoint analyses on the PP population only. However, it was decided that the same model will be used for the secondary and exploratory endpoints as in the primary efficacy endpoint, so the analyses will be done on the ITT Population as well for all efficacy endpoints except DMD-LMS.

9 APPENDICES

9.1 APPENDIX A: Schedule of Assessments

Procedure / Event ¹	Screening	Baseline	Day 1		Week 4	Week 6	Month 3			Month 4.5	Month 6			Month 9			Mo 12 / ET ²	
Trial Day (Visit Window)	$\leq 30\text{ d prior to Rand.}$	$\leq 2\text{ d prior to Day 1}$	1 d	14 d (± 3) post Inf #1	30 d (± 7)	45 d (± 7)	14-30 days pre Inf #2	90 d (± 14)	14d (± 3) post Inf #2	135 d (± 14)	14-30 days pre Inf #3	180 d (± 14)	14d (± 3) post Inf #3	14-30 days pre Inf #4	270 d (± 14)	14d (± 3) post Inf #4	360 d (± 14)	
Intravenous Infusion #			#1					#2				#3			#4			
Informed Consent / Assent	X																	
Demographics	X																	
Medical History	X																	
Eligibility Assessment	X																	
Randomization ³	X																	
Medical Status Questionnaire ⁴	X	X							X			X			X		X	
Prior & Concomitant Medications	X	X	X	X				X	X			X	X		X	X	X	
Adverse Events ⁵	X	X	X	X				X	X			X	X		X	X	X	
IP Intravenous Infusion ⁶			X					X				X			X			
Post-Infusion Safety Call ⁷				X					X				X			X		
DMD Upper Limb PROM	X	X						X				X			X		X	
PODCI	X	X						X				X			X		X	
DMD Lifetime Mobility Scale	X	X						X				X			X		X	
Vital Signs	X	X	X					X				X			X		X	
Height / Ulna Length ⁸	X	X						X				X			X		X	
Weight	X	X	X					X				X			X		X	

[figure not shown]
Procedure / Event ¹	Screening	Baseline	Day 1		Week 4	Week 6	Month 3		Month 4.5	Month 6		Month 9		Mo 12 / ET ²			
Trial Day (Visit Window)	$\leq 30\text{ d prior to Rand.}$	$\leq 2\text{ d prior to Day 1}$	1 d	14 d (± 3) post Inf #1	30 d (± 7)	45 d (± 7)	14-30 days pre Inf #2	90 d (± 14)	14d (± 3) post Inf #2	135 d (± 14)	14-30 days pre Inf #3	180 d (± 14)	14d (± 3) post Inf #3	14-30 days pre Inf #4	270 d (± 14)	14d (± 3) post Inf #4	360 d (± 14)
Physical Examination	X										X					X	
12-Lead ECG		X						X			X			X		X	
Pulmonary Function Testing ⁹	X2	X						X			X			X		X	
PUL 1.2 and 2.0	X	X						X			X			X		X	
Grip Strength	X	X						X			X			X		X	
Pinch Strength (Key and Tip)	X	X						X			X			X		X	
Elbow Flexion Strength	X	X						X			X			X		X	
NSAA (ambulatory subjects only)	X	X						X			X			X		X	
PSC Lab Collection ¹⁰					X		X				X			X			
Serum Chemistry ^{11 12}	X	X			X			X			X			X		X	
Hematology ^{11 13}	X	X			X			X			X			X		X	
Urinalysis ^{11 14}	X	X			X			X			X			X		X	
DMD Genetic Testing ^{11 15}	X																
HLA Typing ¹¹		X															
Donor-Specific Antibodies ¹¹		X			X		X				X			X		X	
Biomarkers ^{16 17}		X			X		X		X		X			X		X	
Exploratory Biomarkers ^{16 18}		X			X		X		X		X			X		X	
Cardiac MRI ¹⁹	X										X					X	

Gray-shaded columns indicate visits that may be performed at either the investigative site or remotely at a designated central laboratory patient service center (see footnote #9)

- 1 Sites will complete assessments in the following sequence: 1) QOL (DMD UL-PROM, PODCI, and DMD-LMS), 2) safety and other trial assessments, excluding blood and urine collections (e.g., vital signs, height, weight, 12-lead electrocardiogram [ECG], etc.), 3) pulmonary function testing (PFT), 4) PUL 1.2 and 2.0, 5) grip strength, 6) pinch strength (key and tip-to-tip), 7) elbow flexion strength, 8) NSAA (if ambulatory), 9) blood and urine collections, 10) cardiac MRI (if applicable), and 11) IP Infusion (if applicable). All efforts must be made for the same clinical evaluator to complete assessments for the same subject at the same time of day throughout the trial (preferably in the morning).
- 2 All attempts must be made to perform the trial assessments indicated for the Month 12 visit (i.e., final comprehensive visit) for subjects that decide to early terminate from the trial before completion and after starting at least one IP infusion.
- 3 Subjects will be randomized between approximately 7 days in advance of their first IP infusion on Day 1. This lead time is to ensure adequate IP shipping times (see IP Manual for shipping specifications). Randomization will be stratified by site and entry item score of the PUL 1.2 at screening. Administration of IP on Day 1 should occur within a maximum of 14 days following randomization; if a delay of more than 14 days between randomization and IP administration is unavoidable, a conversation between the Investigator and Medical Monitor should occur to determine the need for repeat assessments prior to infusion. Subjects that are not randomized may be re-screened at the discretion of the Investigator.
- 4 Updates regarding frequency of wheelchair use, transition to wheelchair full time, ventilatory support, and frequency of falls.
- 5 A blood sample for tryptase should be obtained within 3 hours of the onset of allergic signs or symptoms, and a second red top tube should be drawn within 3 hours of a severe allergic reaction, and frozen at -20°C, for other future analyses.
- 6 All IP infusions will be conducted in an outpatient setting at the investigative site. Prior to each IP infusion, medications will be administered to the subject as determined by the Investigator based on the pre-treatment guidelines provided by Capricor and/or institutional protocols to minimize the risk of potential severe allergic reactions such as anaphylaxis. Subjects will be observed for at least 2 hours post infusion, including pulse oximetry monitoring for at least 30 minutes post infusion. Sites will observe local institutional policies related to parenteral infusions and post-infusion monitoring.
- 7 A safety phone call will be performed 14 days (± 3 days) after each IP infusion, and if clinically indicated, an unscheduled in-person visit will be performed at the investigative site with targeted assessments based on presentation of signs and symptoms.
- 8 Ulna length will be measured in all subjects. Standing height will be measured if a subject is capable. If standing height cannot be measured, height will be calculated using a measurement of ulna length per Section 13.1.2 of the protocol.
- 9 Paired forced-maneuver testing will be performed on Screening Day 1 and Day 2 (approximately 24 hours between testing sessions) to confirm acceptable FVC variance (exclusion criterion 7). PFT testing sequence: SVC, forced maneuver (FEV₁/FVC/PEF), MIP, MEP, PCF, and IFR.
- 10 Blood collections for clinical laboratory and DSA testing at Week 4 and pre-dose DSA testing at Months 3, 6, and 9 will occur either at the investigative site or remotely at a designated central laboratory patient service center.
- 11 Blood and urine samples will be collected using trial-specific laboratory kits, and then shipped to and tested at a central laboratory. Required sample collection for a visit may occur on multiple days; if the visit includes an IP infusion, sample collections should occur prior to IP administration. Baseline blood samples may be collected on Day 1 prior to IP administration to reduce number of venipunctures.
- 12 Basic metabolic panel (Glucose, Sodium, Potassium, Chloride, Bicarbonate, BUN, Creatinine, Calcium), comprehensive hepatic panel (Albumin, Alkaline Phosphatase, Total Protein, ALT, AST, GGT, Direct Bilirubin, Total Bilirubin).
- 13 CBC with WBC differential, hemoglobin, hematocrit and platelet count
- 14 Appearance, bilirubin, color, nitrite, occult blood, pH, protein, specific gravity, glucose, ketones, RBC, and WBC. If required, microscopic analysis of sediment will be performed and reported per occurrence

- 15 DMD genetic testing will be available at screening for subjects who have not previously completed genetic testing or whose historical genetic results were not performed at a CLIA-certified laboratory as determined by an Investigator. The turn-around time for final results may exceed the 30-day screening window; allow 29-49 days for receipt of final test results.
- 16 Week 6 and Month 4.5 blood samples will only be collected at the investigative site.
- 17 Biomarkers may include those of muscle inflammation (osteopontin); systemic inflammation (IL-1 β , IL-2, IL-6, IL-10, TNF- α , CXCL10); muscle damage (troponin I [cardiac, fast skeletal, slow skeletal], troponin T, CK-MM, CK-MB, creatine kinase [total], creatine phosphate, and creatinine); and muscle regeneration (myostatin and follistatin).
- 18 Collected only if separate informed consent and/or assent provided
- 19 Subjects will undergo cardiac MRI if they are physically capable as determined by an Investigator. Subjects that cannot complete a cardiac MRI as part of the trial will complete an echocardiogram at screening using the site's local equipment, acquisition protocol, and evaluation procedures. The reported LVEF from a local interpretation, whether it's measured via cardiac MRI or echocardiogram, will be used to assess eligibility (exclusion criterion 1).

The following analyses are post-hoc. The additional efficacy analyses outlined below were deemed necessary to assess the robustness of inferences from the pre-specified analyses to violations of the normality assumptions in the pre-specified analyses that arose from the smaller-than-planned sample size. For completeness, this Addendum reinstates multiple protocol-specified endpoints previously removed from the final analysis via the Final SAP v3.0. In addition, Adverse Event and cardiac and steroid medication summaries and listings are further detailed in this Addendum.

2. Efficacy Analyses

A parametric linear mixed effects model for repeated measures (MMRM) is the pre-specified analysis for all primary, secondary, and exploratory endpoints of the study. The original study and statistical analysis plan anticipate a total sample size of around 80 subjects. However, the final number of subjects enrolled in the study is 20. Because of the smaller sample size, the primary analysis model is less likely to be robust to departures for certain assumptions¹. Beyond simply identifying if violations of assumptions exist, a critical aspect of model checking is to understand the consequences violations (if present) had on data interpretations².

Specifically, the smaller than intended sample size necessitates increased scrutiny on the assumption of the normality of residuals in the pre-specified primary, parametric MMRM analysis. Concern regarding robustness to departures from normality of the residuals supports the use of additional analyses to supplement the pre-specified model in the HOPE-2 trial.

A common method for dealing with non-normality in a study with less than 30 subjects is to employ a non-parametric test¹. Non-parametric models generally require fewer assumptions than parametric models and therefore inferences from non-parametric models are less dependent on assumptions^{1,2}. However, parametric analyses generally have more power if assumptions are valid, which is also an important consideration when sample size is small. Data transformations can be used to alter the original distribution into a transformed distribution for which the normality assumption is more likely to be valid with small sample sizes while retaining use of a parametric model. Therefore, a data transformation can be used to satisfy normality assumptions without the loss of power inherent to non-parametric methods.

Results from a non-parametric and / or data-transformed analyses can be compared to the corresponding results from a parametric analysis to assess the consequences of departures from assumed conditions. Additional sensitivity analyses can be used to assess the robustness of other aspects of the primary and sensitivity modeling approaches².

2.1. Assessment of Departures from Normality Assumptions and their Consequences in the HOPE-2 Trial

The residuals from the pre-specified model of the primary analysis in the HOPE-2 trial will be plotted in a histogram and inspected visually. An inferential assessment for departure from normality will be implemented via the Shapiro-Wilk test.

A data transformation approach will be implemented that retains as many aspects of the primary analysis as possible. This approach will model changes from baseline (and baseline values) after transforming (converting) them to percentile ranks. The primary model will then be fit to the percentile ranks. The estimates from this alternative analysis will be re-transformed back to the original scale to facilitate interpretation on the original scale.

2.2. Details of the Data Transformed Model

The primary efficacy analysis is change from baseline to Month 12 in the mid-level (elbow) dimension of the PUL 1.2 assessed via a parametric linear MMRM model to compare treatment groups in mean change from baseline to Month 12. If non-normality of the residuals is identified via the procedure identified in Section 2, a data transformation will be applied and then the primary MMRM model will be applied to the transformed data. This primary MMRM model on the transformed data tests the same hypotheses.

$$\begin{aligned} H_0: \mu_C - \mu_P &= 0 \\ H_a: \mu_C - \mu_P &\neq 0 \end{aligned}$$

where μ_C and μ_P are population mean of changes from baseline in CAP-1002- and placebo-treated subjects, respectively, which on the transformed data is also a test of the medians because the mean and the median of a distribution of percentiles are the same.

To implement this model, an MMRM analysis will be used to analyze the percentile ranked primary efficacy endpoint data using the same pre-specified ITT population. Data from the post-baseline visits (Month 3, 6, 9 and 12) will be modelled with visit, treatment, and treatment-by-visit interaction as the main effects, and ranked baseline score, site and binary stratification of entry item score of the PUL 1.2 at screening (2, 3 vs. 4, 5) as covariates. A First Order Autoregressive (AR(1)) covariance structure will be used to model the within-subject errors. The Kenward-Roger's (K-R) approximation will be used to estimate the denominator degrees of freedom. The primary comparison will be the contrast between CAP-1002 and placebo at Month 12.

For a given outcome, this analysis will be implemented by calculating the percentile rank of each change-from-baseline value relative to all observed change-from-baseline values for that outcome (across all subjects and all post-baseline observation times). The percentile ranked change-from-baseline is the dependent variable in the model.

This modeling approach will be applied to primary, secondary, and some exploratory endpoints for the ITT Population only.

In addition, for PUL and Cardiac MRI outcomes, Global Statistical Tests³ (GST) will be calculated as the averaged percentile ranked change-from-baseline.

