7.4. Treatment Assignment

Subjects will be prospectively randomized in stratified permuted blocks in a 1:1 allocation to intravenous infusion of either CAP-1002 or placebo. See Section [9.4](#) for additional details related to randomization.

[figure not shown]

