14. STATISTICS

14.1. General Considerations

The objectives of the trial are to evaluate the safety and efficacy of intravenous infusions of CAP-1002 administered in four doses at 3-month intervals in subjects with DMD and impairment of skeletal muscle function. All statistical tests will be two-sided with 0.05 significance levels. The detailed description of the trial statistical methods is provided in the Statistical Analysis Plan (SAP). Any deviations from the SAP will be described and justified in the final Clinical Study Report.

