6.1 Primary Efficacy Endpoint

The primary efficacy endpoint is change from baseline to Month 12 in the mid-level (elbow) dimension of the PUL 1.2. The hypothesis set to be tested is:

$$H_0: \mu_c - \mu_p = 0$$

$$H_a: \mu_c - \mu_p \neq 0$$

where μ_c and μ_p are population mean absolute changes from baseline in CAP-1002- and placebo-treated patients, respectively.

A MMRM analysis will be used to analyze the primary efficacy endpoint using the ITT population. The results for Month 3, 6, 9 and 12 visits will be modeled with visit, treatment, and treatment-by-visit interaction as the main effects; baseline measurement, site and binary stratification of entry item score of the PUL 1.2 at screening (2, 3 vs. 4, 5) will be included as covariates in the model. An autoregressive (AR(1)) covariance structure will be the covariance structure to model within-subject errors. The Kenward-Roger's (K-R) approximation will be used to estimate the denominator degrees of freedom. The primary comparison will be the contrast between CAP-1002 and placebo at Month 12.

As a supportive analysis, the analysis may be evaluated in the PP population.

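### The percentile-rank MMRM in the SAP Addendum tests neither mean nor median change at Month 12, so it cannot be read as evidence about the mean PUL effect

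*SAP*

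**What the plan says.** SAP 6.1 sets the primary hypothesis on the raw scale. The two parameters are "population mean absolute changes from baseline in CAP-1002- and placebo-treated patients, respectively", compared at Month 12 by an MMRM.

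SAP Addendum 2.2 replaces each change from baseline by its percentile rank among all observed changes for that outcome, pooled over subjects and post-baseline visits. It refits the same MMRM and takes the Month 12 contrast. It states that "This primary MMRM model on the transformed data tests the same hypotheses", writes out the same null and alternative, and again defines the parameters as population means of change. It adds that on the transformed data this is "also a test of the medians because the mean and the median of a distribution of percentiles are the same".

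The opening text of Addendum Section 2 says that transformed results can be compared with the parametric result, to see what departures from the assumptions have done. Addendum 2.1 says the estimates "will be re-transformed back to the original scale to facilitate interpretation on the original scale". No re-transformation method is given.

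**The concern.** A contrast in mean percentile rank is a different quantity from a contrast in mean change, and different again from a contrast in medians. The Addendum adopts the rank model because residuals may be non-normal, and Addendum 2.3.3 speaks of unusual observations behind that non-normality. Skew or outliers concentrated in one arm are a setting in which the three hypotheses can separate.

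The rank model is offered as a robustness check. A reader told that both models test one hypothesis will take agreement as confirmation of the mean effect. The same reader will blame any disagreement on non-normality, when the two models may simply be answering different questions. A re-transformed figure in PUL points invites the same reading. The reach is wide: Addendum 2.2 applies the model to primary, secondary and some exploratory endpoints and builds the global tests on it, and Addendum 2.5 draws forest plots on the transformed scale only.

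**Working it through.** **Inputs.** From the Addendum: "the final number of subjects enrolled in the study is 20". From Protocol 7.4: subjects are "prospectively randomized in stratified permuted blocks in a 1:1 allocation", so about 10 per arm. There are four post-baseline visits (Months 3, 6, 9, 12). The documents give no SD, no distribution and no percentile formula. I assume mid-ranks: percentile = 100 × (rank − 0.5)/N. Covariates are left out; they do not turn a rank contrast into a mean contrast. The plan states no figure here to reproduce, so I start from its premise.

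**1. The premise.** The Addendum's reason is "because the mean and the median of a distribution of percentiles are the same". For N untied values the ranks are 1 to N, so mean and median percentile are both 50. With ties the mean stays at 50 but the median need not. The ten pooled percentiles in step 2 are 5, 35 (five times) and 80 (four times): mean (5 + 175 + 320)/10 = 50, median 35. In any case the premise concerns the whole pool, whereas the test contrasts two arms at one visit.

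**2. Equal means, unequal mean ranks.** CAP-1002 {-2, -2, -2, -2, -2}; placebo {-1, -1, -1, -1, -6}. Both means are -2. Mid-ranks: -6 has 1, each -2 has 4, each -1 has 8.5. Percentiles: 5, 35, 80. Mean percentile for CAP-1002 is 35; for placebo (4 × 80 + 5)/5 = 65.

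**3. Equal medians, unequal mean ranks.** CAP-1002 {-2.5, -2.2, -2, 5, 6}; placebo {-9, -8, -2, -1.5, -1}. Both medians are -2. CAP-1002 ranks 3, 4, 5.5, 9, 10 sum to 31.5, so the mean percentile is 100 × (31.5 − 2.5)/(10 × 5) = 58. Placebo ranks 1, 2, 5.5, 7, 8 sum to 23.5, giving 100 × (23.5 − 2.5)/(10 × 5) = 42.

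**4. What is tested.** If ranking were done within Month 12 with equal arms, the gap in mean percentiles would be 100 × (p − 0.5), where p is the probability that a CAP-1002 change exceeds a placebo change, ties counted half. In step 2, p = 5/25 = 0.20 and the gap is -30, as found. Addendum 2.2 ranks across all visits, so this no longer holds. Take Month 12 placebo {-4, -3, -2, -1} and CAP-1002 {-6, -5, -0.5, 0}: 8 of 16 pairs favour CAP-1002, so p = 0.50. Add 24 earlier-visit values between -1.4 and -0.6, half on each side of -1, so N = 32. Placebo ranks 3, 4, 5, 18 give 100 × (30 − 2)/(32 × 4) = 21.9. CAP-1002 ranks 1, 2, 31, 32 give 100 × (66 − 2)/(32 × 4) = 50.0. The Month 12 null is therefore equal expected pooled percentile rank, which depends on the other visits too.

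**5. With four-visit pooling.** Population values from 100,000 draws per arm. Assumptions: AR(1) correlation 0.7 on the latent normal scale; Months 3, 6 and 9 at 25%, 50% and 75% of the Month 12 change; back-transformation taken as the pooled quantile at each arm's mean percentile.

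| Assumed Month 12 case | Mean difference (CAP-1002 − placebo) | Mean percentile, CAP-1002 / placebo | Back-transformed difference |
|---|---|---|---|
| Equal means: N(-2,1) vs 80% N(-1,1) + 20% N(-6,1) | 0.00 | 26.8 / 41.7 | -0.49 |
| Equal medians, opposite skew | 1.23 | 39.0 / 26.4 | 0.47 |
| Unequal means, equal ranks: N(-1.33,1) vs 80% N(-1,1) + 20% N(-8,1) | 1.07 | 37.1 / 37.1 | 0.00 |
| Pure shift, SD 2 | 1.02 | 48.2 / 32.4 | 0.55 |

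In the pure-shift row, within-arm median percentiles were 41.3 and 20.0 against means of 48.2 and 32.4, so the premise in step 1 fails there as well.

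**The case against.** The Addendum labels these analyses post hoc and supplementary. SAP 6.1 keeps the raw-scale MMRM as primary, and SAP 4.4 treats p-values after the interim as nominal. If the arms have identical distributions, or differ only by a shift, the mean, median and rank nulls coincide. Under identical distributions the rank test held its size: 4.8% at 10 per arm, with a t-test standing in for the MMRM. All of this stands and limits the consequence. It does not make the two sentences true, because the Addendum states no such condition. Reading the parameters as means on the rank scale does not rescue them either: that is no longer the primary hypothesis, and the median argument still fails within an arm.

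A reader might infer that the rank model will produce false support for CAP-1002 in this trial. The documents cannot bear that out. In one assumed equal-mean example (placebo N(0,1); CAP-1002 90% N(0.6,1) and 10% N(-5.4,1)), the rank test favours CAP-1002 in 11% to 12% of trials at 10 per arm against a nominal 2.5%. The raw t-test does so in 8% to 9%, so most of that excess is shared. The clear separation, 39% against about 6% rejection, needs 50 per arm, more than this trial's 20 subjects or the roughly 80 first anticipated. The first case in the table gives 21% against 8.5% two-sided at 10 per arm, but favours placebo. With no SD or distribution in the documents, no rate can be attached to this trial.

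A reader might also infer that the sponsor will present the re-transformed value as a mean difference. No passage says so. The documented gap is that the method is missing.

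**Conclusion.** The claims in Addendum 2.2 that the rank model tests the primary mean hypothesis and the medians are wrong as written. The hand examples settle this with no distributional assumption beyond mid-rank percentiles: 35 against 65 with equal means, and 58 against 42 with equal medians. What is tested is equality of expected percentile rank at Month 12, pooled over arms and visits.

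The practical effect is on interpretation. Comparing this result with the parametric one, and converting it to PUL points by an unstated method, can be misread as evidence about the mean PUL effect. Even under a pure shift of about 1.0 point, one plausible back-transformation returned 0.55; that figure rests on the assumptions in step 5. The primary MMRM and its estimate are untouched, and misreporting is a risk rather than a documented event. The text should be corrected, but the point does not threaten the primary analysis.

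**What to change.** In Addendum 2.2, state the null as equal expected percentile rank at Month 12, with ranks pooled over arms and post-baseline visits as that section defines them. A null of probability 0.5 of a better outcome should be used only if ranking is changed to within visit. Delete the statements that the model tests the same hypotheses and the medians.

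Report the effect on the rank scale with its confidence interval. In Addendum 2.1, specify any back-transformation and label its result as not a mean difference. Take the mean PUL effect only from the raw-scale MMRM in SAP 6.1. A Hodges-Lehmann shift may be added, labelled as unadjusted and as relying on a pure shift.

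The cost is a change of wording, one interval and possibly one extra estimate, with no new data. The supportive claim becomes slightly weaker, because agreement between the two models no longer counts as confirmation of one hypothesis.
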